Dose evaluation will be guided by safety and PK profiles. Safety will be assessed by review of AEs, including DLTs; clinical laboratory tests, and vital signs. Anticancer activity will be evaluated using bone scan and computed tomography (CT) of the chest, abdomen, and pelvis, per Prostate Cancer Clinical Trials Working Group 3 (PCWG3).

The recommendations of the PCWG3 will be used to determine response ([Scher et al. 2016](#)). Tumor assessments will include ^{99m}Tc-methylene diphosphonate radionuclide bone scintigraphy and CT of the chest, abdomen, and pelvis within 28 days before the first dose of enzalutamide (for Dose-Determination Phase Segment 1) and/or CORT125281 (for Dose-Determination Phase Segment 2 and Expansion Phase) and at intervals of 8 weeks after the first dose of study treatment for the first 24 weeks. Thereafter, tumor assessments will occur at intervals of 12 weeks until disease progression. Objective responses will be confirmed no less than 4 weeks after the criteria for response are first met (if possible, 4–6 weeks). PSA, alkaline phosphatase (ALP), and lactic dehydrogenase (LDH) will be assessed at the Baseline/Screening Visit and Day 1 of each cycle. Results will be documented in the electronic case report form (eCRF). Tumor assessments will be documented until disease progression. Documentation of overall survival including subsequent therapies with duration and response will continue every 4 months until 2 years from the date that the last patient enrolls in the study or until all patients have completed follow-up for radiographic disease progression (whichever is later).

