6.7 Exploratory Measures of Anticancer Activity

Response to treatment will be determined using PCWG3 recommendations ([Eisenhauer et al. 2009](#); [Scher 2016](#); [Appendix B](#)).

Radiologic tumor assessments: CT of the chest, abdomen, and pelvis, and ^{99m}Tc-methylene radionucleotide bone scintigraphy should be performed within 28 days prior to the first dose of enzalutamide (for Dose-Determination Phase Segment 1) and/or CORT125281 (for Dose-Determination Phase Segment 2 and the Expansion Phase). CT scan with ≤5-mm axial slices is advised for all patients. A cross-sectional magnetic resonance imaging (MRI) scan of the abdomen and pelvis, with a non-contrast CT scan of the chest is acceptable for patients who are intolerant of contrast. To ensure comparability, the baseline radiographs/scan, and subsequent radiographs/scans to assess response, should be performed using consistent methods and identical techniques. The same method (radiological or physical) should be employed and assessed by the same individual on each occasion, if possible. Radiographic tumor assessments should be performed every 8 weeks from the first dose of study treatment (CORT125281 or on-study enzalutamide, whichever is earlier) for the first 24 weeks and every 12 weeks thereafter, at

the EOT Visit (if not performed within 4 weeks), and as clinically indicated. For on-study scans, a window of ± 14 days is acceptable with the timing of the scans based on Cycle 1 Day 1. The rPFS per PCWG3 will be assessed.

Blood-based markers: PSA, ALP, and LDH will be assessed during the Baseline/Screening Visit, Day 1 of each cycle, and EOT Visit. Results will be documented in the eCRF.

Survival: Patients will be followed for survival every 4 months until 2 years from the date that the last patient enrolls in the study.

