9.5.5 Analyses of Anticancer Activity

The following endpoints will be summarized to meet the study secondary objective of characterizing preliminary efficacy:

- ORR, defined as the proportion of patients with an objective tumor response (either partial response [PR] or complete response [CR] per Investigator using Response Evaluation Criteria in Solid Tumors version 1.1[RECIST v1.1]) in patients with measurable disease, including best radiographic response for soft tissue
- A reduction in PSA level by $\geq 50\%$
- Distribution of the best PSA response
- Time to SSE defined as symptomatic fracture, radiation or surgery to bone, or spinal cord compression

- rPFS defined as the time from the first dose of study treatment (CORT125281 and/or enzalutamide) to the date when the first site of disease is found to progress on CT, MRI, or radionucleotide bone scan per PCWG3, or death whichever occurs first. Progression will be assessed by the Investigator using RECIST v1.1. The proportion of patients who are progression-free at 4, 6, and 12 months will also be summarized.
- DOR, defined as the time from the first occurrence of a documented objective tumor response to the time of radiographic progression (per Investigator using RECIST v1.1) or death from any cause on study, whichever occurs first
- Time to PSA progression, clinical progression (per Investigator), and bone disease progression
- Overall survival, defined as the time from the first dose of study treatment (CORT125281 and/or enzalutamide) to the date of death from any cause

Data summaries will include number, percent and waterfall displays as appropriate. Time-to-event endpoints will be characterized using Kaplan-Meier method.

For the analyses of rPFS and DOR, data for the patients who have not experienced disease progression or death will be censored at the time of the last tumor assessment date.

Data for the analysis of overall survival will be censored at the time of the end of follow-up period. Dose adjustments/changes in enzalutamide will be summarized by CORT125281 dose and overall.

The change in markers of disease status, such as PSA and CTCs, will be compared between the Lead-In Period and Cycle 1, when possible.

These analyses will be performed in the Safety Population and Response-Evaluable Population.

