8.11. Interim Analyses or Timing of Analyses

The DRC consisting of Investigators, the Medical Monitor, a Clinical Pharmacologist, and additional members as appropriate will review the safety, PK, and PD data following the

completion of each cohort during Dose-Determination Phase Segment 1, after all patients have completed 3 cycles of treatment in Dose-Determination Phase Segment 2, and at least every 6 months during the Expansion Phase.

An interim safety analysis will be conducted after a total of 20 patients complete 3 cycles of therapy in the Expansion Phase. If at any time during the Expansion Phase the DLT rate exceeds 33%, the dose will be declared non-feasible, and no additional patients will be enrolled to that dose. A lower dose level may be evaluated, per the recommendation of the DRC.

9. Efficacy Analyses

The recommendations of the PCWG3 will be used to determine disease response for this study. Tumor assessments include ^{99m}Tc -methylene diphosphonate radionucleotide bone scintigraphy and CT of the chest, abdomen, and pelvis. Baseline tumor assessment will be performed within 28 days before the first dose of enzalutamide (for Dose-Determination Phase Segment 1) and/or the first dose of exicorilant (for Dose-Determination Phase Segment 2 and Expansion Phase). Post-baseline tumor assessments will be performed every 8 weeks after the first dose of enzalutamide and/or exicorilant for the first 24 weeks. Thereafter, tumor assessments will occur at intervals of 12 weeks until disease progression. Objective responses will be confirmed no less than 4 weeks after the criteria for response are first met (if possible, 4 – 6 weeks). PSA, alkaline phosphatase (ALP), and lactic dehydrogenase (LDH) will be assessed at the Baseline/Screening Visit and Day 1 of each cycle. The ITT population will be used to address the secondary and exploratory efficacy objectives of the study. Disease response and progression assessed according to RECIST v1.1 by the Investigator will provide the basis for efficacy endpoints.

At all scheduled visits, data recorded for target, non-target, and new lesions, and Investigator response assessment will be presented in by-patient listings. Summary tables and figures will be provided for endpoints as described in the following sections. Response rate endpoints will be summarized by providing the point and interval estimates. Time-to-event variables will be summarized using Kaplan-Meier estimates and plots.

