9.1. Secondary Efficacy Endpoints

Objective Response Rate (ORR): Patient listings of tumor response outcomes (CR, PR, non-CR/non-progressive disease, stable disease, progressive disease, unevaluable, or not assessed) at study visits, as well as best overall response per RECIST v1.1, will be presented by treatment regimen dose group and overall for the ITT population. By-group summary tables will include distribution of response outcomes, best overall response derived over all visits, and point estimates with Clopper-Pearson² 95% CIs for ORR, defined as the proportion of patients with an objective tumor response (either PR or CR) in patients with measurable disease, including best radiographic response for soft tissue.

For supportive purposes, best overall response and point estimates with Clopper-Pearson 95% CIs for ORR will also be summarized using confirmed response.

PSA Levels: PSA levels recorded at each visit will be listed. Proportions of patients in the Safety population who experience a 50% or greater reduction in PSA levels at any visit since baseline will be reported with Clopper-Pearson 95% CIs by treatment group and overall. Mean reduction levels will be characterized via summary statistics. Median time from date of first dose of exicorilant to PSA progression (first occurrence of 50% or greater increase in PSA levels), along with 95% CIs will be estimated via Kaplan-Meier method, and also plotted graphically by treatment group. Patients who are alive and progression-free will be censored at the date of their-last PSA evaluation.

In dose escalation and expansion phases separately, best PSA response will be illustrated graphically via waterfall plots. For each patient, the maximum percent change in PSA levels since baseline will be depicted on the response axis, with vertical bars below the baseline representing decline in the blood-based marker.

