Patients who had 2 or more consecutive missed scheduled tumor assessments immediately prior to disease progression	Date of the last adequate tumor assessment without evidence of disease progression before the 2 missed tumor assessments and on or before the data cutoff date
Patients who did not have disease progression as determined by the Investigator and died more than 119 days from most recent tumor assessment.	Date of the last adequate tumor assessment on or before the data cutoff date

Note: If a patient meets the criteria for more than 1 censoring rule, PFS will be censored at the earliest censoring date.

Kaplan-Meier curves will be plotted by treatment regimen dose groups, and the estimate of median rPFS time (months) with 95% CI will be ascertained. For each cohort, progression-free rate at 4, 6, and 12 months will also be summarized.

Duration of response (DOR): Duration of response will be defined for patients in the Response-Evaluable population as the time from the first occurrence of a documented objective tumor response of CR or PR to the time of radiographic progression (per Investigator using RECIST v1.1) or death from any cause on study, whichever occurs first. Patients who have not experienced disease progression or death will be censored at the time of the last tumor assessment date. Date of censoring will be determined according to same rules as described for rPFS endpoint.

$$\text{DOR (months)} = (\text{earliest date of progression, death, or censoring} - \text{date of first documented objective response} + 1) / 30.4375$$

Kaplan-Meier graph will be plotted by treatment group and estimates of median duration with 95% CIs will be obtained for each dose cohort and overall. Patients who do not achieve a tumor response of CR or PR, will be excluded from this analysis.

Clinical progression: For the Response-Evaluable population, clinical disease progression, defined as time from first dose of study treatment (exicorilant and/or enzalutamide) to date of treatment discontinuation due to disease progression, will be estimated via the Kaplan-Meier

method. Patients who are alive and progression-free will be censored at their end of study visit. Median time to progression and associated 95% CIs will be summarized, overall and by treatment group. Kaplan-Meier graph of the probability of the event will also be plotted by treatment group.

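### SAP 9.1 bases the main ORR, best overall response and the DOR set on unconfirmed responses, at odds with the confirmation rule stated in Protocol 3.1 and SAP 9

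*SAP*

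**What the plan says.** **Confirmation rule.** Protocol 3.1 (Overall Design) states: "Objective responses will be confirmed no less than 4 weeks after the criteria for response are first met". The introduction to SAP Section 9 (Efficacy Analyses) carries the same sentence without exception.

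**Main response analysis.** SAP 9.1 plans summary tables with "best overall response derived over all visits, and point estimates with Clopper-Pearson" 95% intervals for ORR. No confirmation condition is attached. It then adds: "For supportive purposes, best overall response and point estimates with Clopper-Pearson 95% CIs for ORR will also be summarized using confirmed response".

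**Protocol definition.** Protocol 9.5.5 reads: "ORR, defined as the proportion of patients with an objective tumor response (either partial response [PR] or complete response [CR] per Investigator", by RECIST v1.1, in patients with measurable disease. It does not use the word confirmed.

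**DOR.** SAP 9.1 measures it as "the time from the first occurrence of a documented objective tumor response of CR or PR" to radiographic progression or death, and leaves out only patients who never reach CR or PR. Protocol 9.5.5 starts DOR at the same point.

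**Scan schedule and assessor.** SAP Section 9: "Post-baseline tumor assessments will be performed every 8 weeks after the first dose of enzalutamide and/or exicorilant for the first 24 weeks", and every 12 weeks after that. Protocol 6.7 allows 14 days either side of the scheduled date. The assessor is the Investigator: "Disease response and progression assessed according to RECIST v1.1 by the Investigator will provide the basis for efficacy endpoints".

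**The concern.** The SAP states a rule for objective responses and then gives the analysis that meets it second rank, without saying why. It never calls the main analysis unconfirmed. That follows because a separate confirmed summary would otherwise have no purpose.

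The Expansion cohorts have about 20 patients each, no concurrent control and open-label treatment, and ORR uses only the patients with measurable disease. A single low reading of the sum of diameters can therefore move the headline rate visibly. The error goes one way: every confirmed responder is also an unconfirmed responder, so the unconfirmed rate can never be the lower of the two.

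For DOR the gap is wider. The supportive summary covers best overall response and ORR only, so no planned DOR analysis leaves out single-scan responders.

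**Working it through.** The plan states no figure that depends on ORR, so there is none to reproduce. The check has four parts.

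**1. Passages side by side.**

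| Item | Confirmation required? |
|---|---|
| Protocol 3.1, general rule | Yes, at least 4 weeks later |
| SAP 9 introduction, general rule | Yes, at least 4 weeks later |
| Protocol 9.5.5, ORR and DOR definitions | Not mentioned |
| SAP 9.1, main ORR and best overall response | No condition |
| SAP 9.1, supportive ORR and best overall response | Yes |
| SAP 9.1, DOR | No condition, no confirmed version |

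An example is PR at week 8 and progression at week 16. This patient counts in the main ORR but not in the confirmed one. He also enters the DOR analysis, with (56 + 1)/30.4375 = 1.9 months by the SAP's formula.

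**2. Can the scheduled scans confirm a response?** The closest that two 8-weekly scans can fall is a late week-8 scan and an early week-16 scan: (112 − 14) − (56 + 14) = 98 − 70 = 28 days, exactly 4 weeks. After week 24 the smallest gap is 84 − 28 = 56 days. The next scheduled scan always qualifies.

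**3. How many false responders could one scan create?** The documents give no measurement error, so the CV of the sum of diameters is an assumption, taken as 10%, 15% and 20%. The model has log-normal error on the baseline and on scans at weeks 8, 16 and 24. PR is a sum at or below 70% of baseline (Protocol Appendix B), and confirmed means two consecutive such scans.

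A hand check at 10%: the log-scale SD of one scan is √ln(1.01) = 0.0998, so a scan-to-baseline difference has SD 0.0998 × √2 = 0.141. A single scan then falls below the threshold with probability Φ(ln 0.7/0.141) = Φ(−2.53), about 0.6%. Three scans sharing a baseline give slightly less than three times that.

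Simulated share of patients counted as responders (2,000,000 per setting):

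| True change | CV | Unconfirmed | Confirmed | Difference (points) |
|---|---|---|---|---|
| None | 10% | 1.6% | 0.1% | 1.5 |
| None | 15% | 10.9% | 1.7% | 9.2 |
| None | 20% | 22.1% | 5.0% | 17.1 |
| 5% growth per scan | 10% | 0.3% | 0.0% | 0.3 |
| 5% growth per scan | 15% | 4.5% | 0.4% | 4.0 |
| 5% growth per scan | 20% | 12.9% | 2.1% | 10.7 |

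At 10% with no true change, the excess is 1.5% × 10 = 0.15 patients in an assumed 10 with measurable disease, or 0.3 in 20.

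Plausibility check on the CVs: with no true change, the same model puts at least one scan 20% or more above the running minimum in 37%, 60% and 72% of patients at CVs of 10%, 15% and 20% (ignoring the 5-mm rule in Appendix B). The two higher CVs would thus call most stable patients progressing.

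**4. What one extra responder does to the reported interval** (Clopper-Pearson 95%; group sizes assumed):

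- 10 measurable: 0/10 = 0% (0 to 30.8%); 1/10 = 10% (0.3 to 44.5%).
- 20 measurable: 0/20 = 0% (0 to 16.8%); 1/20 = 5% (0.1 to 24.9%).

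**The case against.** The strongest reply is that the SAP follows the protocol. The protocol defines ORR and the start of DOR without mentioning confirmation, and its confirmation sentence stands among scan intervals and PSA timing, not in an endpoint definition. On that view the SAP added a confirmed analysis and demoted nothing. This stands in part. A reader might infer an undeclared change that SAP Section 13 should have listed, and the documents do not support that. The general rule still appears in both documents, though, and in the SAP it introduces the efficacy analyses, so the two passages need reconciling.

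Second, confirmed ORR is already planned with its interval, and responses by visit are listed, so a careful reader can recover both rates. That holds for ORR and best overall response. It does not hold for the DOR estimates.

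Third, a reader might infer that false responders would feed a go decision. They would not. Protocol 9.3 makes the analyses estimation only, the Expansion thresholds in Protocol 9.4.2 rest on PSA response, and the primary objective rests on DLTs.

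Fourth, a reader might take the 11% and 22% figures as the expected inflation. They come from assumed CVs found nowhere in the documents, under which most stable patients would also be called progressing.

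Fifth, single-scan responders tend to shorten median DOR, so they do not flatter that endpoint. This is correct: the fault in DOR is an unclear set, not a favourable bias.

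**Conclusion.** The inconsistency is real. Both documents say that responses will be confirmed, while the main ORR, best overall response and DOR set in SAP 9.1 do not require it. The consequence is limited to a headline ORR that may be too high in small uncontrolled cohorts, and a DOR set that mixes confirmed and single-scan responders.

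The direction for ORR is certain. The size is not: about 1.5 points at an assumed 10% CV with no true change, about 0.3 points with 5% growth per scan, and more at higher CVs. These figures assume log-normal error, three scans, and no stopping of scans at progression. No test, threshold or dose decision is affected. It should be corrected before the analysis, but it does not undermine the trial's conclusions on dose or PSA response.

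**What to change.** In SAP 9.1:

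- Make confirmed response, with the second scan at least 4 weeks after the first, the basis of the main ORR, best overall response and DOR set. State that the next scheduled scan qualifies.
- Date DOR from the first of the two scans.
- Show the unconfirmed ORR, best overall response and DOR as supportive, and label them unconfirmed.

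If the sponsor prefers to keep the present order, the minimum is to label the main ORR unconfirmed, give the reason, explain how this fits the confirmation sentence in SAP Section 9, and say which responders enter DOR.

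The cost is SAP wording and one added DOR summary; both ORR versions are already planned, and no imaging is added. The headline ORR may be slightly lower, and a true responder with no later scan, for example after withdrawal or at data cutoff, would count as unconfirmed. The supportive table keeps such patients visible.

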6.3.5 Adverse Events

Details on definitions and reporting of AEs are provided in Section 8.

All AEs will be recorded from the time of signing of the ICF until 30 days after the final dose of study treatment (CORT125281 or enzalutamide, whichever is later).

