7.5 Post-Treatment Follow-Up Period

If the patient discontinued CORT125281 and enzalutamide for reasons other than disease progression, tumor assessments will be collected and documented until disease progression.

All patients will continue to be followed until the study endpoints are met (radiographic disease progression, SSE, and overall survival). Phone follow-up for overall survival (ie, the date and cause of death, and post-treatment information) will continue every 4 months until 2 years from the date that the last patient enrolls in the study or until all patients have completed follow-up for radiographic disease progression (whichever is later).

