7.5.2 Every 4 Months After the End-of-Treatment +30 Days Visit (\pm 10 Days)

- Record post-treatment anticancer therapies, dates of initiation, end dates, and response
- Record survival information (ie, date and cause of death), unless the patient requests to be withdrawn specifically from the study survival follow-up. This request must be documented in the patient's medical record and signed by the Investigator. The study staff may use public information source (such as county records) to obtain information about survival status only per local regulations, as appropriate.
- For patients who discontinued the CORT125281 + enzalutamide due to reasons other than disease progression, continue tumor assessments and PRO and QoL questionnaires per the schedule of procedures until disease progression

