Symptomatic Skeletal Event (SSE): SSE is defined as symptomatic fracture, radiation or surgery to bone, or spinal cord compression. SSEs include only symptomatic events of clear clinical significance. Kaplan-Meier estimates of median time from date of first dose of exicorilant to the first occurrence of SSE and associated 95% CIs, will be computed by treatment regimen dose group and overall for the Safety population. Patients who are event-free will be censored at the date of their end of study/treatment + 30 days visit. Kaplan-Meier graph of the probability of the event will also be constructed by treatment group.

Radiographic progression-free survival (rPFS): For the Response-Evaluable population, rPFS will be determined from the first dose of study treatment (exicorilant and/or enzalutamide) to the date when the first site of disease is found to progress on CT, MRI, or radionucleotide bone scan per PCWG3, or death, whichever occurs first. Progression will be assessed by the Investigator using RECIST v1.1.

$$\text{rPFS (months)} = (\text{earliest date of progression, death, or censoring} - \text{date of first study treatment} + 1) / 30.4375$$

Patients who do not experience disease progression or death (due to any cause) will be right-censored at the time of the last tumor assessment date. Censoring date will be based on the date patient was last known to be alive and progression-free (i.e., last assessment date) or data analysis cutoff date, whichever occurs first. Censoring rules are summarized in [Table 3](#) below.

Table 3: Censoring Rules for the Primary Analysis of PFS

Censoring Categories	Date of Censoring
Patients who did not have baseline or postbaseline tumor assessments and did not die on or before the data cutoff date	Date of first study treatment

Patients who did not have disease progression as determined by the Investigator and did not die on or before the data cutoff date	Date of the last adequate tumor assessment on or before the data cutoff date
Patients who did not have disease progression as determined by the Investigator on or before initiation of subsequent anticancer therapy for prostate cancer and did not die on or before the data cutoff date	Date of the last adequate tumor assessment on or before initiation of subsequent anticancer therapy and on or before the data cutoff date

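### Time to SSE: the SAP sets no end to the event window but appears to censor event-free patients at EOT +30 days, so any late SSE that is counted biases the Kaplan-Meier estimate

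*SAP*

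**What the plan says.** Protocol 9.5.5 lists the endpoint among the secondary efficacy measures: "Time to SSE defined as symptomatic fracture, radiation or surgery to bone, or spinal cord compression". SAP 9.1 plans "Kaplan-Meier estimates of median time from date of first dose of exicorilant to the first occurrence of SSE and associated 95% CIs", by treatment regimen dose group and overall, in the Safety population. It names no date after which an SSE ceases to count. For patients without an event it says: "Patients who are event-free will be censored at the date of their end of study/treatment + 30 days visit".

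Protocol 7.5 describes a longer follow-up: "All patients will continue to be followed until the study endpoints are met (radiographic disease progression, SSE, and overall survival"). The phone follow-up for survival "will continue every 4 months until 2 years from the date that the last patient enrolls in the study", or until radiographic follow-up is complete if that is later.

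The content of the 4-monthly contact is set out in Protocol 7.5.2: "Record post-treatment anticancer therapies, dates of initiation, end dates, and response", and "Record survival information (ie, date and cause of death), unless the patient requests to be withdrawn specifically from the study survival follow-up". For patients who stopped treatment without progression, tumor assessments and questionnaires also continue. Neither this list nor Table 16 has an SSE item. Protocol 6.3.5 ends the other natural route of capture: "All AEs will be recorded from the time of signing of the ICF until 30 days after the final dose of study treatment". Protocol 7.5.1 waives the EOT +30 Days Visit when the EOT Visit already falls 30 or more days after the last dose.

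**The concern.** The event definition and the censoring rule cover different periods. Take two patients who stop treatment on the same day. One has an SSE eight months later that becomes known; as the SAP reads, he is an event at that late date and stays in the risk set until then. The other is seen event-free over the same eight months, yet leaves the risk set at EOT +30 days. Off-treatment time is therefore kept or discarded according to whether an event later occurred. That conditions on the future, and Kaplan-Meier estimation assumes it does not happen.

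Capture of late SSEs is also uneven. Radiation to bone can surface in the subsequent-therapy record. Symptomatic fracture, bone surgery and cord compression have no named collection point once adverse-event recording stops. The reported medians, confidence intervals and curves would then depend partly on which late events happened to be written down. SAP 9.1 avoids this for its neighbouring endpoints: OS is censored at last contact, and rPFS at the last adequate tumor assessment.

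**Working it through.** The documents give no SSE rate, median or power, so there is no stated figure to reproduce. The size of the effect has to rest on assumptions.

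**Assumed inputs (none from the documents).** SSE hazard h = 0.02 per month. Treatment time exponential with mean 6 months, plus 1 month to reach EOT +30, giving T. Total follow-up C uniform from 18 to 30 months. A fraction c of SSEs after T becomes known.

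**Rule applied.** SSEs up to T count. Later SSEs count if recorded. Everyone else is censored at T.

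**True value with unchanged hazard.** SSE-free at 12 months = exp(-0.02 × 12) = 78.7%; at 18 months, exp(-0.02 × 18) = 69.8%.

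**Why the estimate moves.** Before month 18, with G = P(T > t), the hazard that Kaplan-Meier sees at month t is

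h·e^(-ht)·[G + c(1 - G)] ÷ {e^(-ht)·G + c(1 - G)·P(t < SSE time ≤ C)}.

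All recorded late events enter the numerator. Of the off-treatment patients, the denominator holds only those who will later have a recorded event. At t = 12, G = exp(-11/6) = 0.160, e^(-0.24) = 0.787 and P(12 < SSE time ≤ C) = 0.166. With c = 0.25:

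- numerator: 0.02 × 0.787 × (0.160 + 0.25 × 0.840) = 0.00582
- denominator: 0.787 × 0.160 + 0.25 × 0.840 × 0.166 = 0.161
- apparent hazard: 0.00582 ÷ 0.161 = 0.036 per month, against a true 0.020

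With c = 0 the extra terms vanish and the apparent hazard is 0.020, so there is no bias.

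**12-month SSE-free estimate under the SAP rule (simulation):**

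| Hazard off treatment | Late SSEs recorded | True | SAP rule | Bias (points) |
|---|---|---|---|---|
| Unchanged | 0% | 78.7% | 78.7% | 0 |
| Unchanged | 10% | 78.7% | about 76.5% | about -2 |
| Unchanged | 25% | 78.7% | 73.7% | -5 |
| Unchanged | 100% | 78.7% | 65.8% | -13 |
| Doubled | 0% | 70.1% | 78.7% | about +9 |

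The last row arises because, with no late SSE recorded, the estimate reflects only the on-treatment hazard, while the true curve falls faster after treatment stops. At 18 months with unchanged hazard, the estimate is about 54.6% at 25% capture and 39.6% at full capture, against a true 69.8%.

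**Sensitivity to the assumptions.** A second set used median treatment of 4 or 6 months, median time to SSE of 15 or 24 months, and 24 months of follow-up. The 12-month bias was about -3 to -6 points at 25% capture and -8 to -13 at 100% with unchanged hazard. It was +9 to +14 points with doubled hazard and no capture.

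**The case against.** The best defence is that the SAP nowhere says late SSEs count. Adverse-event recording stops 30 days after the last dose, which matches the censoring point, so the endpoint could be meant as on-treatment plus 30 days. If so, and the hazard does not change off treatment, the bias is zero. This is a fair reading of the intent. It is not written down, however, and it sits badly with a protocol that follows patients until SSE. One sentence would settle it.

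The slash in the censoring phrase could also admit an end-of-study date, which would reduce the asymmetry. EOT +30 is likelier: Amendment 5 replaced the combined end-of-study/early-termination label with EOT (Protocol Appendix E), and SAP 9.1 refers separately to an end of study visit for clinical and bone progression. That two readings are possible is itself a reason to reword.

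Capture at the contacts cannot be excluded entirely. Protocol 7.5 mentions post-treatment information without defining it, and SAP 9.1 cites a Long-Term Follow-Up eCRF that is not among the documents.

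On importance, SSE is descriptive, with no test or decision rule. In a 20-patient cohort the sampling error at 12 months is about 1.96 × √(0.787 × 0.213 ÷ 20) = ±18 points, well above a 5-point bias. That lowers the severity. It does not remove the error, because the confidence interval does not reflect it.

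Three stronger inferences are tempting and should not be drawn:

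- That the curve always falls too fast. The doubled-hazard row shows the opposite.
- That beyond treatment end the risk set holds only patients known to have an event. Treatment lengths differ: with 25% capture, 0.787 × 0.160 ÷ 0.161, about 78%, of those at risk at month 12 are still within their own EOT +30 window.
- That a waived EOT +30 visit leaves no possible censoring date. The EOT Visit itself, or last dose plus 30 days, is an obvious substitute; the SAP only needs to name it.

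**Conclusion.** The concern holds as a mismatch between event window and censoring. As written, and on the likelier reading of the censoring phrase, the time-to-SSE estimate is biased whenever any late SSE is counted. Under the assumed 2% monthly hazard and mean 6 months on treatment, the 12-month bias runs from 0 (no late SSE recorded, hazard unchanged) to -13 points (all recorded). It is about +9 points if the hazard doubles off treatment and none is recorded. Neither the size nor the direction can be fixed from the documents, since both depend on the off-treatment hazard and on how many late SSEs become known. A reader might take the full-capture figures as the expected effect; the schedule does not support that, because most SSE types have no collection route after EOT +30, so low partial capture is more plausible. Nor does the point reach the trial's main conclusions: dose selection rests on DLTs, and the expansion cohorts are sized on PSA response. It is worth correcting, at lower severity, because time to SSE is a named secondary endpoint and the correction is cheap.

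**What to change.** Make the event window and the censoring date match, by one of two routes.

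**(a) SAP wording only.** In SAP 9.1, count only SSEs up to 30 days after the last dose of study treatment. Censor all other patients at the earliest of that date, last contact and data cutoff, and label the endpoint on-treatment. This also covers a waived EOT +30 visit and patients still on treatment at cutoff. The cost is that late SSEs are not used and, if the hazard rises off treatment, the SSE-free rate is overstated, as in the doubled-hazard row.

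**(b) Preferred.** Add SSE type and date to the 4-monthly contact in Protocol 7.5.2 and Table 16. In SAP 9.1, censor event-free patients at the last date SSE status was ascertained. This matches the follow-up that Protocol 7.5 already promises. The cost is a small protocol and eCRF change. It may not recover SSE status from contacts already made, which matters because SAP 8.8 describes the Segment 1 cohorts as already enrolled. If recovery proves poor, use (a) for those patients' cohorts and say so.
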